## **H. Viral resistance**

Tenofovir resistance is defined phenotypically as: (1) rise in serum HBV-DNA levels to levels above  $10^4$  IU per ml (by quantitative PCR) after they had fallen below this level during therapy in patients who have been compliant with their regimen and genotypically as (2) documented mutation/s in the reverse transcriptase region of the HBV polymerase gene (thus far the only documented mutation is rtA194T), and biochemically as (3) rise in serum aminotransferases to twice the upper limit of normal range. Patients who develop resistance will be continued on the therapy if they agree to stay on therapy and if serum aminotransferases and HBV-DNA are consistently lower than pretreatment levels or changed to other available agents if clinically indicated.

Emtricitabine resistance in this study can only be defined phenotypically as a rise in serum aminotransferases to twice the upper limit of normal range. Genotypic resistance is defined by the typical mutations in the conserved catalytic region of the HBV polymerase gene (YMDD region).

Monitoring for mutations in the reverse transcriptase domain of the HBV-DNA polymerase on combination therapy will be performed on serum samples obtained at baseline, and yearly on all serum samples that have detectable HBV DNA from patients receiving tenofovir plus emtricitabine and tenofovir monotherapy. The monitoring will be done by sequence analysis of the reverse transcriptase region of the HBV DNA polymerase gene and will be performed by LDB, NIDDK. Novel mutations will be correlated with the clinical response. Antiviral susceptibility and cross resistance testing using in vitro assays will be conducted by Gilead Sciences using stored serum samples. Resistance data will be submitted to the FDA according to the FDA guidance document entitled, "Guidance for submitting HBV Resistance Data."

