- 1) Will combination therapy yield a higher response rate and prevent the development of further resistance than monotherapy in patients with previous antiviral resistance (lamivudine, adefovir and entecavir)? Response will be defined as HBV DNA  $<10^2$  IU/ml and normal ALT at 48 and 192 weeks. Samples of blood at yearly intervals that are HBV DNA positive will be tested for tenofovir (rtA194T) and emtricitabine (rtM204V/I and rtL180M) resistant mutations by direct sequencing. The investigators believe that the maintained virological and biochemical response will be higher in the combination arm compared to the monotherapy arm and the rate of further resistance will be lower at 48 and 192 weeks.

Patients who relapsed after withdrawal of lamivudine, adefovir or the combination of lamivudine plus adefovir:

- 1) We hypothesize that combination therapy will result in a greater proportion of subjects re-responding to re-institution of therapy. Response will be defined as an HBV DNA  $<10^2$  IU/ml and normal ALT at 48 and 192 weeks. For individuals who experienced HBeAg sero-reversion (HBeAg negative to positive) a response will also include loss of HBeAg or HBeAg seroconversion again. We further hypothesize that

combination therapy will prevent or delay the appearance of antiviral resistance compared to tenofovir monotherapy in persons who relapsed? To address this issue, the HBV polymerase gene will be sequenced from all serum samples at yearly intervals that are HBV DNA positive.

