#### A1. Inclusion criteria: Primary Study (nucleoside analogue-naïve subjects)

- 1) Age >18 years and older, male or female
- 2) Known serum HBsAg positivity for 24 weeks
- 3) Detectable HBV DNA > $10^4$  IU/ml. For patients with cirrhosis HBV DNA > $10^3$  IU/ml
- 4) Serum ALT or AST levels 1.5 X ULN (for ALT:  $\geq 62$  U/L and for AST:  $\geq 46$  U/L) based on at least two determinations taken at least one month apart during the 24 weeks before study entry; no ALT requirement for patients with cirrhosis
- 5) Liver biopsy within 2 years of entry that is consistent with chronic hepatitis and with a histology activity index (HAI) score of 4 or more (scores range from 0-18) and an Ishak fibrosis score of at least 1 (scores range from 0-6). For patients who have had a liver biopsy at another institution, slides must be obtained for reading and scoring at the NIH.
- 6) Written informed consent

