#### **D. Treatment**

Patients will be stratified for randomization on the basis of HBeAg status and on the basis of previous therapy. The primary study will be in patients (Groups A and B) who have not been previously treated (treatment naïve) and who have active liver disease (based on ALT levels and liver biopsy) and high levels of HBV DNA ( $>10^4$  IU/ml). The salvage study will be in patients (Groups C and D) who have received other nucleoside analogues and who continue to have HBV DNA detectable in serum ( $>10^2/10^3$  IU/ml, respectively). A total of 100 patients will be enrolled including at least 60 patients total in Groups A and B and up to 40 patients in Groups C and D (previously treated).

**Group A:** Up to 20 patients with detectable HBeAg in serum and no previous therapy with nucleoside analogues.

**Group B:** Up to 20 patients without detectable HBeAg in serum and no previous therapy with nucleoside analogues.

**Group C:** Up to 20 patients who have previously received lamivudine, adefovir or entecavir therapy but who have persistence of HBV DNA in serum as detected by PCR-based assay ( $>10^2$  IU/ml) and HBeAg in serum for at least six months.

**Group D:** Up to 20 patients who have previously received lamivudine, adefovir or entecavir therapy but who have persistence of HBV DNA in serum as detected by PCR-based assay ( $>10^2$  IU/ml) and absence of HBeAg in serum for at least six months.

**Group E:** Up to 20 patients who have previously received lamivudine, adefovir or the combination of lamivudine and adefovir and who relapsed after therapy was stopped

After medical evaluation, liver biopsy and informed written consent, patients will be randomized in double-blind fashion to receive either combination therapy with tenofovir and emtricitabine or mono-therapy with tenofovir. Patients with anti-viral resistance to lamivudine adefovir, entecavir or telbivudine or multi-drug resistance will continue on pre-study medication until the day of randomization. Randomization will be done by random numbers kept by the Pharmaceutical Developmental Service of the Clinical Center (A1-20, B1-20, C1-20, D1-20, E1-20). Both tenofovir (300 mg tablets) and Tenofovir (300 mg) / emtricitabine (200 mg) will be provided by Gilead Sciences. A 12 week supply of medications will be provided. Compliance will be monitored by medication diaries and counting of the residual tablets returned at outpatient visits.

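### Phenotypic emtricitabine resistance is defined by an aminotransferase rise alone, so a virally suppressed combination patient can be counted as resistant

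*Combined protocol and SAP*

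**What the plan says.** Section H (Viral resistance) treats the two drugs differently.

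- **Tenofovir** has three numbered items. The first opens "Tenofovir resistance is defined phenotypically as: (1) rise in serum HBV-DNA levels to levels above" 10^4 IU/ml and applies "after they had fallen below this level during therapy in patients who have been compliant with their regimen". The second is a documented polymerase mutation. The third is "biochemically as (3) rise in serum aminotransferases to twice the upper limit of normal range". The text does not say whether the items are required together or are three separate kinds of resistance.
- **Emtricitabine** has one phenotypic rule: "Emtricitabine resistance in this study can only be defined phenotypically as a rise in serum aminotransferases to twice the upper limit of normal range". A genotypic rule, based on YMDD-region mutations, stands separately.

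Section D randomizes patients "to receive either combination therapy with tenofovir and emtricitabine or mono-therapy with tenofovir", so emtricitabine is given in one arm only. Section H provides for sequencing at baseline and then yearly, in both arms, on samples with detectable HBV DNA. Under Hypotheses and Issues, one question for previously resistant patients is whether combination therapy will "prevent the development of further resistance than monotherapy". The test named there is direct sequencing.

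**The concern.** Aminotransferases measure liver injury, not viral replication. A resistance rule built on them alone counts any rise to 2 × ULN, whatever its cause and whatever the HBV DNA level. Nothing in the emtricitabine sentence requires viral rebound, an earlier fall in ALT, a second sample or adherence to treatment.

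Non-viral rises are foreseeable. Section G lists increased liver enzymes among the post-approval events for tenofovir. It also reports ALT above 5 × ULN in 2% of emtricitabine patients against 1% of comparators in 48-week HIV studies, a higher threshold than the one used here.

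At stake is the meaning of any phenotypic resistance rate from this trial. Section H says that resistance data will go to the FDA, and no section says which definition a reported rate will use.

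**Working it through.** **1. The plan's only power figure.** Section I gives 86% power for 94% against 70% full virological response, two-sided Fisher's exact test at 0.05, 50 per arm. Exact enumeration of both binomials gives 85.7%, so the figure reproduces. It concerns the primary virological endpoint and does not depend on any resistance definition.

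**2. The rules side by side.**

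| Rule | HBV DNA rise | Prior viral response | Compliance | Repeat sample | Aminotransferases |
|---|---|---|---|---|---|
| Emtricitabine phenotype (H) | none | none | none | none | 2 × ULN |
| Tenofovir item 1 (H) | above 10^4 IU/ml | had fallen below 10^4 | required | none | none |
| Tenofovir item 3 (H) | none stated | none stated | none stated | none stated | 2 × ULN |
| Breakthrough (F) | at least 1 log10 from nadir | initial full virological response | required | two in a row, a month or more apart | none |
| Resistance leading to a switch (D) | above 10^6 IU/ml | none stated | none stated | none stated | twice above normal |

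Only the emtricitabine phenotype and tenofovir item 3 have no viral element. Item 3 is labelled biochemical; the emtricitabine rule is labelled phenotypic.

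**3. Can another measurement correct a false label?** Take a combination patient with undetectable HBV DNA and ALT at 2 × ULN. Section F puts the upper end of normal ALT at 41, so the threshold is 2 × 41 = 82 U/L. The phenotypic rule is met. The sample has no detectable HBV DNA, so it is not sequenced, and no on-treatment sequence exists to contradict the call. Visits fall at weeks 2, 4, 8, 12, 24, 36 and 48 (7), then every 12 weeks to week 192 ((192 − 48)/12 = 12). That makes 19 post-baseline tests, and one high value is enough.

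**4. Which arm is affected?** This depends on how tenofovir items 1 to 3 combine.
- All required: a monotherapy patient with only an ALT rise is not resistant under any rule, while the combination patient is. A phenotypic comparison is skewed against the combination.
- Separate types: the same ALT rise is biochemical tenofovir resistance in both arms. The skew shrinks, but the non-viral criterion now reaches both arms.

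**5. Illustration of size (rates assumed, none from the documents).** If 2, 5 or 10% of 50 combination patients have such a rise by week 192, the expected false calls are 50 × 0.02 = 1, 50 × 0.05 = 2.5 and 50 × 0.10 = 5. Suppose these calls were pooled with genotypic ones, and the items are all required so that monotherapy gains none. The protocol's expectation for naïve patients is 20 to 25% genotypic resistance on monotherapy and none on combination at 4 years. Fisher power for that comparison would be:

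| Per arm | Monotherapy rate | 0% false | 2% | 5% | 10% |
|---|---|---|---|---|---|
| 50 | 20% | 95% | 78% | 51% | 20% |
| 50 | 25% | 99% | 93% | 75% | 41% |
| 20 | 20% | 37% | 27% | 17% | 7% |
| 20 | 25% | 59% | 45% | 30% | 14% |

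The rows with 20 per arm correspond to the 40 naïve patients for whom the expectation is stated. The rows with 50 extend it to 100 patients. No section plans such pooling, so the table shows only what pooling would cost.

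**The case against.** The strongest reply is that a reader might infer bias in the trial's planned resistance comparison, and the documents do not support that. The naïve-patient hypothesis compares mutation rates. The hypothesis for previously resistant patients rests on direct sequencing. The major secondary endpoint in Section F is freedom from failure of therapy and from resistance mutations, and the three on-treatment failure types defined there use HBV DNA. Section I plans no phenotypic resistance analysis. This stands in full.

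A reader might also infer that false calls can arise in the combination arm alone, with none possible on monotherapy. Tenofovir item 3 uses the same threshold for a drug given in both arms, so that inference holds only if the three items are jointly required. The text does not settle this.

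A third tempting inference is that a false label would move suppressed patients off their assigned drug. The sentence in Section H on continuing or changing treatment sits in the tenofovir paragraph and allows a change only when clinically indicated. Section D ties switching for resistance to HBV DNA above 10^6 IU/ml as well as raised aminotransferases, by mutual agreement. A suppressed patient does not meet the Section D condition. What remains is that Sections D, F and H describe resistance or failure differently.

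Nor do all naïve and relapsing patients start just below the threshold. Entry for them is by "Serum ALT or AST levels 1.5 X ULN", so AST may qualify a patient, and naïve patients with cirrhosis have no ALT requirement. Alcoholic liver disease and nonalcoholic steatohepatitis are excluded at entry, which removes some non-viral causes but not new ones.

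One rationale for the rule is that viral rebound on two drugs cannot be assigned to either of them. An aminotransferase rise cannot be assigned either; sequencing can.

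**Conclusion.** The definition is faulty as written: it labels a virally suppressed combination patient with a non-viral aminotransferase rise as emtricitabine-resistant, and the sequencing plan cannot reverse the label. This follows from the text and needs no assumption. The consequence is limited to phenotypic resistance rates that are reported alone or pooled with genotypic calls. The direction of error between arms depends on whether the tenofovir items are joint, which is not stated.

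The size is unknown. A reader might attach a yearly rate and quote a count of false calls, but the documents give no rate of non-viral rises to 2 × ULN in this population. The HIV figures in Section G use a higher threshold in a different disease. The emtricitabine hepatitis B trial figures do not separate viral from non-viral rises. The 1 to 5 of 50 in the illustration rests wholly on an assumed 2 to 10%.

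The primary endpoint, its 86% power and the mutation-based comparisons stand. This merits correction before any resistance rate is reported, but it does not threaten the trial's main conclusions.

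**What to change.** For analysis purposes:

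1. Use one HBV DNA-based phenotypic definition in both arms. The breakthrough rule in Section F is a ready candidate, since it already asks for two consecutive samples and absence of non-compliance. It covers only patients with an initial full virological response, so say how later or partial responders who rebound are classified.
2. Attribute a rebound to tenofovir or emtricitabine by sequencing.
3. Report aminotransferases of 2 × ULN or more only as a biochemical descriptor alongside virological rebound.
4. State whether tenofovir items 1 to 3 are joint or separate.
5. State which definition feeds each reported resistance rate, and that phenotypic and genotypic calls are tabulated separately.

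Sections D, F and H must also be reconciled on what counts as resistance for continuing or changing treatment. No clinical rule is proposed here.

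The cost is a wording change. Section E already has HBV DNA measured at every visit on therapy, and Section H already has viraemic samples sequenced yearly. A rebound between yearly points may need its stored sample sequenced.

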## I. Statistical analysis

Superiority of combination therapy compared to monotherapy with tenofovir will be tested. The primary analysis will be conducted at 1 and 4 years on the entire study cohort (Groups A-D). A separate analysis will be conducted on previously treated subjects with resistance combining all HBeAg-positive and -negative cases. We predict the rate of full virological response to combination therapy will be 94% and to tenofovir monotherapy to be 70% at 4 years. A Fisher's exact test with a .05 two-sided significance level will have 86% power to detect the difference between a combination therapy proportion of  $\pi_1$  of .94 and a monotherapy proportion of  $\pi_2$  .70 if the sample size in each group is 50. Secondary analyses will be done within the HBeAg positive and negative stratum and the nucleos(t)ide naïve and nucleos(t)ide treated stratum. Variables to be analyzed in association with a virological response will include: baseline ALT and HBV DNA level, liver histology, HBV genotype and previous resistance. Patients with missing data or who drop out of the study will be considered as treatment failures on an intention to treat basis. For comparison of means, Student's t-test will be used. All reported p-values will be 2-sided.

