### Précis

Chronic hepatitis B is a major cause of cirrhosis, end-stage liver disease and hepatocellular carcinoma and affects approximately 1.25 million Americans. Six medications have been licensed for use in chronic hepatitis B in the United States, but their relative benefit and long-term efficacy remain unclear. In previous studies, we have shown that maintained suppression of HBV DNA can be achieved with nucleoside analogues and that suppression is associated with marked improvements in disease. In this randomized study, we propose to evaluate long-term therapy with tenofovir alone or in combination with emtricitabine (FTC). Forty treatment-naïve patients with chronic hepatitis B will be enrolled in the primary study. After medical evaluation and liver biopsy, patients will be stratified by hepatitis B e antigen (HBeAg) status and randomized to receive either tenofovir alone or in combination with FTC. Treatment will be continued long-term (at least four years) and patients will be carefully monitored for side effects, serum aminotransferase and HBV DNA levels. Patients will undergo repeat liver biopsy and assessment of antiviral resistance at 1 and 4 years. The primary endpoint of therapy will be the maintained suppression of HBV DNA to below  $10^2$  IU/ml (lower limit of detection of current assays). The study will assess the relative efficacy and safety of combination versus mono-therapy. A separate group of 60 previously treated patients will also be enrolled and randomized to mono- or combination-therapy to assess the safety profile of these agents. The primary analysis will be conducted on the entire study cohort.

[Word count = 250]

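### Section I names Groups A-D as the primary analysis set (at most 80 patients under the Section D caps) but bases its power on 100; Group E was most likely left out by mistake

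*Combined protocol and SAP*

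**What the plan says.** Section I (Statistical analysis) defines the primary analysis set in one sentence: "The primary analysis will be conducted at 1 and 4 years on the entire study cohort (Groups A-D". It then gives 86% power for a two-sided Fisher's exact test at .05, with full virological response of 94% on the combination and 70% on monotherapy at four years, "if the sample size in each group is 50".

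Section D (Treatment) defines five groups. Group A is "Up to 20 patients with detectable HBeAg in serum and no previous therapy with nucleoside analogues"; Groups B, C and D carry the same ceiling of 20. Group E is "Up to 20 patients who have previously received lamivudine, adefovir or the combination of lamivudine and adefovir and who relapsed after therapy was stopped". The randomization lists match these ceilings: "A1-20, B1-20, C1-20, D1-20, E1-20".

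Two other statements in Section D leave Group E out. The enrolment sentence gives 100 patients "including at least 60 patients total in Groups A and B and up to 40 patients in Groups C and D". The salvage label reads "The salvage study will be in patients (Groups C and D) who have received other nucleoside analogues".

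Elsewhere, the Précis plans 40 treatment-naïve patients and adds: "A separate group of 60 previously treated patients will also be enrolled and randomized to mono- or combination-therapy". It places the primary analysis on the full cohort and names no groups. The Background counts relapsers among the salvage patients and says that those patients enter the primary comparison. The opening paragraph of the Protocol section lists a minimum of 40 naïve, a maximum of 40 experienced and a maximum of 20 relapsed patients within 100. Section A.3 gives relapsers their own salvage-study inclusion criteria.

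**The concern.** The sentence in Section I disagrees with itself: it claims the whole cohort, then lists four of the five groups. It also disagrees with the sample size that follows, because Groups A to D cannot supply 50 per arm under the caps and lists in Section D.

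The parenthesis is the only place where Section I names the groups in the primary test. Because the salvage label in Section D also omits Group E, a reader could take the omission as deliberate. An analyst could then include or drop up to 20 of 100 randomized patients, all of them relapsers, and find text in support of either choice. The Protocol section says that investigators and patients are not blinded, although Section D describes randomization as double-blind. If treatment is open, that choice could be made after results by arm are visible. Applied literally, the label would also mean that the stated 86% does not describe the test performed.

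**Working it through.** **Inputs.** From Section I: two-sided Fisher's exact test, significance level .05, response rates .94 and .70, 50 per arm, and dropouts counted as failures, so every randomized patient stays in the denominator. From Section D: five groups capped at 20, with five lists of 20. Equal allocation is inferred from the equal arm sizes in the power statement.

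**Counts.**
- Groups A-E: 5 × 20 = 100 = 2 × 50.
- Groups A-D: 4 × 20 = 80 = 2 × 40.
- Précis: 40 naïve + 60 previously treated = 100. Under the caps, A + B = 40 and C + D + E = 60, so the Précis total needs Group E.
- Section D enrolment sentence: 60 + 40 = 100 in A-D. The caps allow only 20 + 20 = 40 in A and B, and the sentence leaves no room for Group E within 100.

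**Power formula.** For arm sizes n₁ (combination) and n₂ (monotherapy),

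power = Σₓ Σᵧ Bin(x; n₁, .94) × Bin(y; n₂, .70) × 1{two-sided Fisher p(x, y) ≤ .05},

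summed over all x from 0 to n₁ and y from 0 to n₂.

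**Reproducing the plan's figure.** With n₁ = n₂ = 50 the sum is .857, so the stated 86% is confirmed. The pooled normal approximation gives 89.0%; the plan's figure is the exact one.

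**Label taken literally.** With n₁ = n₂ = 40 the sum is .768 (pooled normal approximation 81.0%). The loss is 85.7 − 76.8 = 8.9 points.

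**Is the drop an artefact of the test's discreteness at 40/40?** Exact power moves unevenly with arm size, so the same sum was run over near-balanced splits. The span of five patients either side of equality is a choice made here and is not in the plan.

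| Total | Splits (combination/monotherapy) | Lowest | Highest | Mean |
|---|---|---|---|---|
| 80 | 35/45 to 45/35 | 76.8% (40/40) | 81.6% (41/39) | 79.0% |
| 100 | 45/55 to 55/45 | 85.7% (50/50) | 89.3% (53/47) | 88.4% |

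The difference in means is 88.4 − 79.0 = 9.4 points, so a loss of about 9 points holds at equal arms and on average. For a total of 80, type II error runs from 100 − 81.6 = 18.4% to 100 − 76.8 = 23.2%.

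**The case against.** The strongest reply is that the documents largely settle the question. Section I speaks of the whole cohort before the parenthesis, the Précis repeats this without restriction, the Background puts salvage patients (relapsers included) in the primary analysis, and 50 per arm needs all 100. On that reading no power is lost, and the 86% is not an arithmetic error.

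There is further support for loose labelling. Section D gives the salvage HBV DNA threshold as 10²/10³ for Groups C and D respectively, yet defines both groups with 10². The pair matches the criteria for experienced patients (A2) and relapsers (A.3), so C and D in that sentence may be meant to cover relapsers. This is inference, but it makes a deliberate exclusion of Group E less likely.

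It can also be said that 100 patients could come from A-D. The Section D enrolment sentence says so outright. The Protocol section's minimum of 40 naïve patients, with only a ceiling on relapsers, would allow more than 80 outside Group E.

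The first two arguments stand as reasons to read the set as A-E, and the two readings are not evenly balanced. They do not remove the contradiction in the sentence that defines the primary set. The last argument does not rescue the label: the enrolment sentence breaks the caps and lists in its own section, and the Protocol section's minimum fits those caps only if exactly 40 naïve patients enrol. That 100 needs Group E is therefore a statement about the Section D caps and lists, which are the operative allocation.

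**Conclusion.** The concern holds. It is a fault in the definition of the primary analysis set, not in the power calculation. Groups A-E is the better-supported reading, and on it the 86% is correct (85.7%) and only the label is wrong. That the omission is a mistake is an inference, which the sponsor should confirm.

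If A-D is meant literally, power falls to 76.8% at 40 per arm, and to about 79% on average over near-balanced splits of 80. This assumes that all four groups fill to 20 and that the 94% and 70% rates still apply without the relapsers. The point should be fixed because it decides which patients enter the primary test; the 9-point loss arises only on the less likely reading.

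**What to change.** - **Section I:** replace Groups A-D with Groups A-E, in line with the Précis, the Background and 50 per arm. If A-D is intended, state that Group E is excluded and why, and restate power as about 77% at 40 per arm.
- **Section D:** add Group E to the salvage label. Reconcile the 60/40 enrolment sentence with the caps, the lists and the 40/60 split in the Précis.
- **Protocol section:** in the same edit, reconcile its minimum of 40 naïve patients with the ceiling of 20 + 20 in Groups A and B.
- **Record:** date the clarification and state whether any comparison by arm had been seen when it was made.

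Naming A-E is a change of wording, with no extra patients and no change to the stated power. Keeping A-D costs about 9 points of stated power at 40 per arm.

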The primary study endpoints will be a maintained full virological response after 48 weeks and 192 weeks of therapy (the two points of formal statistical analysis). The major secondary endpoint will be absence of a failure of therapy and absence of resistance mutations. Other endpoints to therapy will be loss of HBeAg, loss of HBsAg, normalization of serum ALT, improvements in histology activity index, improvements in hepatic fibrosis, improvement in Fibroscan scores and decrease in HVPg. Other endpoints will be improvement in symptom scores at 48 and 192 weeks.

Failure of therapy may be due to primary non-response, lack of virological response, breakthrough, or relapse, as defined below.

A **primary non-response** is defined as lack of decrease in HBV DNA levels by at least 1  $\log_{10}$  after at least 24 weeks of therapy in the absence of non-compliance.

A **failure in virological response** is defined as failure to suppress HBV DNA below  $10^4$  IU/ml after 48 weeks of therapy in the absence of non-compliance.

A **breakthrough** is defined as a  $\geq 1 \log_{10}$  IU/L increase in HBV DNA level from nadir in two consecutive samples at least one month apart in a patient with an initial full virological response in the absence of non-compliance.

A **relapse** is defined as a rise in HBV DNA levels to above  $10^4$  IU/ml or of ALT to above the normal range after therapy is stopped in a patient who previously had a maintained full virological response.

These definitions are all interlocking but help to define response and non-response rates and whether therapy has a sustained effect.

**Stopping therapy:** Therapy will be continued indefinitely or until one of the following endpoints are reached:

1. **Failure of therapy:** If HBV DNA levels remain consistently  $>10^4$  IU/ml after one year of continuous therapy, patients will be offered alternative therapy or the option to stop therapy. Alternative therapies may include switching to combination therapy if they were receiving monotherapy or switching to entecavir if receiving combination therapy. Patients who fail to respond may also elect to receive a course of peginterferon. These options are available at the NIH Clinical Center on an open-label basis.

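### Efficiency improvement, not an error: name a stratified CMH test for the primary comparison in place of the pooled Fisher test (about 5 to 6 points more power at 50 per arm), and settle alpha for weeks 48 and 192 in the same edit

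*Combined protocol and SAP*

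**What the plan says.** Section D, Treatment: "Patients will be stratified for randomization on the basis of HBeAg status and on the basis of previous therapy". The random numbers are held as five lists, "A1-20, B1-20, C1-20, D1-20, E1-20". Groups A to D separate naïve from experienced patients and HBeAg-positive from HBeAg-negative patients. Group E (relapsers) is not split by HBeAg.

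Section I, Statistical analysis, states a superiority aim and a cohort: "The primary analysis will be conducted at 1 and 4 years on the entire study cohort (Groups A-D"). The design assumption is "We predict the rate of full virological response to combination therapy will be 94% and to tenofovir monotherapy to be 70% at 4 years". Fisher's test appears only in the power sentence, "exact test with a .05 two-sided significance level will have 86% power to detect the difference", with 50 patients in each arm. The strata enter only here: "Secondary analyses will be done within the HBeAg positive and negative stratum", and likewise for naïve versus treated patients. Student's t-test is named for means. Dropout is handled by one rule: "Patients with missing data or who drop out of the study will be considered as treatment failures".

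Section F, Assessment of response, defines the primary endpoint as "maintained full virological response after 48 weeks and 192 weeks of therapy (the two points of formal statistical analysis"). Neither section says how the .05 is shared between the two analyses.

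**The concern.** Three points arise together.

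- **No test is assigned to the primary comparison.** Fisher's test is implied by the power sentence but not stated as the analysis.
- **The implied test ignores the groups used for randomization, and it is conservative.** With binary data at 40 to 50 per arm, Fisher's actual type I error lies well below .05. Power is left unused in a trial of at most 100 patients followed for 192 weeks.
- **There are two formal primary analyses and no alpha rule.** Fisher's slack happens to hold down the chance of at least one false positive. A test that uses its full 5% would remove that accidental protection, so the test and the alpha rule have to be settled together.

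At stake is efficiency and clarity of the primary analysis, not the validity of Fisher's p-values.

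**Working it through.** **Inputs.** From Section I: 94% versus 70%, two-sided .05, 50 per arm. From Section D: five lists of 20, hence about 10 per arm per list if balanced. For Groups A-D at 20 each, 80 patients or 40 per arm. The documents give no stratum-specific rates and no within-patient correlation, so these are varied as assumptions.

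**1. The plan's own figure.** Power = Σ b(x; 50, .94)·b(y; 50, .70) over all pairs (x, y) with Fisher p ≤ .05. The result is 85.7%, so the stated 86% is reproduced. At 40 per arm it is 76.8%.

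**2. Fisher's true size at nominal .05.** The same sum with equal rates gives:

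| Common rate | .70 | .82 | .90 | .94 |
|---|---|---|---|---|
| 50 per arm | 3.1% | 2.7% | 1.8% | 1.0% |
| 40 per arm | 2.8% | 2.8% | 1.7% | 0.7% |

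The maximum over all rates is 3.5% (50 per arm) and 3.3% (40 per arm).

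**3. CMH without continuity correction.** In stratum k, x is the number of responders on combination, m the responders in both arms, n1 and n0 the arm sizes, and N = n1 + n0. The statistic is [Σ(x − m·n1/N)]² / Σ[n1·n0·m·(N − m) / (N²(N − 1))], compared with 3.84. Power comes from 400,000 simulated trials with 10 per arm per stratum. The heterogeneous rates below average .70 and .94.

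- Five strata: monotherapy .50, .85, .60, .80, .75; combination .88, .98, .92, .97, .95.
- Four strata: monotherapy .50, .85, .60, .85; combination .88, .98, .92, .98.

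| Scenario, alpha .05 | Fisher | Chi-square | CMH | CMH − Fisher | CMH − chi-square |
|---|---|---|---|---|---|
| 5 strata, same rates | 85.8% | 91.9% | 91.1% | +5.3 | −0.8 |
| 5 strata, different rates | 86.4% | 92.4% | 92.5% | +6.1 | +0.1 |
| 4 strata, same rates | 76.8% | 84.5% | 84.3% | +7.5 | −0.2 |
| 4 strata, different rates | 77.9% | 85.5% | 86.6% | +8.7 | +1.1 |

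The last column isolates stratification, which moves power by at most about one point here. The rest of the gain comes from leaving Fisher's conservatism. Uneven filling of the lists (15, 15, 8, 8, 4 per arm) gives 91.1% with the same rates and 93.5% with different rates.

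**4. Size of CMH.** It is 4.9 to 5.2% at common rates .70 to .90, and 4.6 to 4.9% at .94. It rises to 5.2-5.3% at .60 and 5.6-5.7% at .50. With strongly prognostic strata under the null (assumed .55, .97, .65, .97, .96), size is 1.2% for Fisher, 2.9% for chi-square and 5.0% for CMH. Here stratifying matters: it keeps the size near nominal.

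**5. Two analyses at .05 each, 50 per arm, rate .82.** If independent, 1 − (1 − size)²:

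- Fisher: 1 − (1 − .0267)² = 5.3%.
- CMH: 1 − (1 − .0498)² = 9.7%.

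With assumed within-patient correlations of .5 to .9, the figures are 5.0 to 3.8% for Fisher and 9.1 to 7.0% for CMH.

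**6. CMH power at week 192 under each alpha rule.**

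| Rule | 50 per arm | 40 per arm |
|---|---|---|
| Week 192 alone at .05 | 91.1-92.5% | 84.2-86.6% |
| .01 at week 48, .04 at week 192 | 89.3-90.9% | 81.0-84.0% |
| .025 at each | 85.3-87.2% | 74.8-78.8% |
| Fisher at .025, for comparison | 78.8-79.4% | 63.1-63.8% |

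At independence and rate .82, the chance of any false positive with CMH is 4.8% under .01/.04 and 4.9% under .025/.025.

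**The case against.** The natural reading of Section I is that Fisher is the primary test, and preferring an exact test at this sample size is legitimate. That stands, and it is why this is an improvement and not an error.

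The gain comes mainly from swapping an exact test for an asymptotic one. That also stands. Against Boschloo's unstratified exact test (89.1% at 50 per arm, 80.9% at 40), Fisher loses only 3.4 and 4.1 points, and a fully exact stratified test reaches only 86.2 to 88.0% at 50 per arm. CMH can slightly exceed 5% when response rates are low, and counting dropouts as failures could push rates down.

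The gain is fragile in two ways. With a continuity correction, CMH power is about 85% at 50 per arm and 74% at 40 with homogeneous strata, so nothing is gained. With an equal alpha split, CMH only restores roughly the planned 86%. Even then it stays more than 6 points above Fisher at the same alpha.

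The alpha rule and the cohort conflict are larger issues than the choice of test. This is true of the cohort: the fall from 86% to 77% comes from A-D versus A-E, not from the test.

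Timing is the last objection. A 12-year study ending in 2019 implies a start near 2007, yet the background cites a 2013 report, so week 48 data may already exist. Section "Protocol" describes the trial as unblinded and Section D as double-blind. A late move to a less conservative test could look data-driven. The timing is inferred, so this does not undo the point, but it bears on how the change is documented.

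**Conclusion.** The point holds as an efficiency improvement. The 86% is correct for Fisher at 50 per arm, and Fisher is valid. Naming an uncorrected CMH test on the randomization groups would raise power by 5.3 to 6.1 points at 50 per arm, or 7.5 to 8.7 points at 40, at one analysis at .05. That full gain over the planned test requires week 192 to be the sole primary analysis. A .01/.04 split keeps most of it at 50 per arm, and .025/.025 uses about all of it.

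These figures assume the plan's 94% and 70%, balanced lists of 20, and the illustrative stratum rates shown. Stronger strata would increase the gain: a separate simulation with a common odds ratio gave 94.1 to 94.9% for strong strata at 50 per arm. The 40-per-arm figures take the group caps of 20 at face value. Section D also gives a count of at least 60 in A-B and up to 40 in C-D, which does not fit those caps.

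**What to change.** In Section I, state the primary test: CMH without continuity correction, stratified by the randomization groups in the primary cohort. Report a Mantel-Haenszel stratum-adjusted risk difference with a 95% confidence interval (simulated coverage .940 to .950 with the Sato variance). Keep Fisher's exact test as a sensitivity analysis.

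In the same edit, do one of the following:

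- Make week 192, the time point that carries the power statement, the single primary analysis at .05, with week 48 secondary.
- Split alpha, for example .01 at week 48 and .04 at week 192.

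Also reconcile whether the primary cohort is Groups A-D, as Section I says, or A-E, which 50 per arm requires under the list sizes. Record the date of the change and what comparative data had been seen by then.

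The cost is SAP wording and minor programming. The trade-offs are:

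- Size is slightly above 5% if common rates fall to .60 or below.
- From the week 192 power ranges above, a .01/.04 split costs about 2 to 3 points and an equal split about 5 to 9 points.
- If week 192 is the sole primary analysis, a week 48 result is not confirmatory.

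If guaranteed type I error control is preferred, Boschloo's unstratified test at 89.1% power (50 per arm, .05) is the alternative.
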